6.3.5 Vital signs

Summary statistics by disease subgroup, dose cohort and scheduled time point will be presented for each vital sign. The change from baseline will also be presented.

Summary statistics for baseline blood pressure (BP) and change from baseline (pre-dose on each study day to post-dose timepoints) will be presented by dose level for each study day. The mean maximum change from baseline (pre-dose on each study day to post-dose timepoints) will also be presented by dose levels for each study day. In case BP is collected on both arms, the average value will be taken for the analyses.

The number of patients with values outside marked reference ranges (shown below) will also be tabulated by disease subgroup, dose cohort and scheduled time point.

The vital signs marked reference ranges are:

Diastolic Blood Pressure (DBP): < 60 mmHg or > 100 mmHg.

Systolic Blood Pressure (SBP): < 80 mmHg or > 180 mmHg.

Pulse: < 40 beats/min or > 120 beats/min.

Temperature: <36.0 5 degree Celsius or >38.5 degree Celsius.

Vital sign assessments will be presented for each patient in a data listing.

6.3.6 ECG results

A summary of clinically significant findings from the 12-lead ECG (CRF data) will be provided for each disease subgroup, dose cohort and time point using a shift table. For this analysis, if the findings for the three assessments at Cycle 1 Day 1 pre-dose are different, the baseline will be defined as the worst assessment prior to first dose intake (if Cycle 1 Day 1 assessments are not done, screening assessments will be used as baseline). For each post-dose time point, the worst assessment of the three triplicates will be taken for the analysis.

The 12-lead ECG results (RR interval and QT interval corrected for heart rate (Fridericia correction) (QTcF) interval reported in the CRF) and changes from baseline will be summarized using standard descriptive statistics by disease subgroup, dose cohort and scheduled time point. The mean of the three ECGs measurements taken at each time point will be used for the summary. For this analysis, the baseline value will be defined as the mean of the three ECGs measurements taken prior to first dose intake.

The same analysis will be repeated on central ECG data (Heart rate (HR), RR, PR, QRS, QT, QTcB, QTcF)

ECG results will be presented for each patient in a data listing.

Outlier analysis:

The number and percentage of patients with maximum on-treatment value of QT/QTc intervals, categorized as ≤ 450 msec, >450 msec and ≤ 480 msec, >480 msec and ≤ 500 msec, and >500 msec, as well as maximum on-treatment change from baseline value of QT/QTc intervals, categorized as <5 msec, >5 msec and <10 msec, >10 msec and <20 msec, >20 msec and <30 msec, >30 msec and <60 msec, and >60 msec will be tabulated based on scheduled and unscheduled 12-lead ECG measurements (CRF and central ECG data).

The following abnormalities will also be tabulated:

- PR abnormality: PR increase from baseline $\geq 25\%$ when $PR > 200$ msec
- QRS abnormality: QRS increase from baseline $\geq 25\%$ when $QRS > 100$ msec
- HR abnormality: HR decrease from baseline $\geq 25\%$ when $HR < 50$ bpm, or $\geq 25\%$ increase when $HR > 100$ bpm.

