 - In patients undergoing intra-patient dose escalation or dose reduction on D1, D8 and D15 of Cycles 1 and 2 after intra-patient escalation to a new dose level: prior to, and at 2 h and 4 h after, [first] intake of BAL101553 study medication. From the third cycle onwards, ECGs will only be obtained pre-dose on Day 1.
 - Triplicate 12-lead ECG should also be obtained when patients experience SBP \geq 180 mmHg or DBP \geq 110 mmHg, or whenever clinical cardiovascular signs or symptoms occur.

ECG from Screening; D1 of Cycles 1, 2; and any abnormal ECG; must be transmitted to a central ECG laboratory for evaluation (including QTc assessment).

- 7. Chest X-ray: to establish a baseline for safety assessments; to be repeated as clinically indicated. For tumor assessments a chest CT scan should be performed. If a chest CT is performed, then a chest X-ray is not required. Radiology assessments conducted within 35 days prior to D1 of Cycle 1 do not need to be repeated during Screening (see Section 5.6).
- 8. Hematology must be performed and reviewed (see Section 5.5.7.1):
 - within 72 hours of first administration of BAL101553 on D1 of Cycle 1
 - within 24 hours prior to D1 of any subsequent Cycle
 - within 24 hours prior to administration of BAL101553 on D8, D15 and D22 of Cycle 1 and Cycle 2
 - within 24 hours prior to administration of BAL101553 on D15 of all Cycles from Cycle 3 onwards.
- 9. Biochemistry must be performed according to the same schedule as Hematology (see Section 5.5.7.2).
- 10. Coagulation and urinalysis must be performed and reviewed within 72 hours of first administration of BAL101553 on D1 of Cycle 1. Coagulation and urinalysis must also be performed and reviewed within 24 hours prior to [first] administration of BAL101553 on D1 of all subsequent Cycles (see Sections 5.5.7.4 and 5.5.7.5).
- 11. Cardiac troponin must be performed and reviewed within 72 hours of first administration of BAL101553 on D1 of Cycle 1. Cardiac troponin must also be performed and reviewed within 24 hours prior to administration of BAL101553 on D8, D15 and D22 of Cycle 1, and Cycle 2. The same test (cardiac troponin-I or troponin-T) must be used consistently for a given patient at Screening and throughout the study (see Section 5.5.7.3).

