5.5.5 Electrocardiograms

5.5.5.1 Phase 1

ECGs must be performed in accordance with Table 8.

Standard, triplicate, 12-lead ECG must be performed using the pre-programmed device provided by the Sponsor. Measurements should be separated by ~1 min and be taken within a 5 min time window. During PK assessments, ECG recordings must be obtained within the 5 min prior to PK blood sampling. ECG measurements will be made at the following time points:

- Screening: to determine eligibility of patients.
- Day 1 of Cycles 1 and 2: pre-dose; 1 h, 2 h, 4 h, and 8 h after [first] BAL101553 dosing
 For cohorts using a q12h dosing regimen, triplicate ECG will be also be obtained at 14 h (i.e., after the second daily dose) after first dosing on Day 1 of Cycles 1 and 2 (Phase 1).
- Days 8 and 15 of Cycles 1 and 2: pre-dose; 2 h and 4 h after [first] BAL101553 dosing.
- Day 1 of Cycle 3 and all subsequent cycles: pre-dose.
- End of Study visit.
- Triplicate 12-lead ECG should also be obtained when patients experience SBP ≥ 180 mmHg or DBP ≥ 110 mmHg, or whenever clinical cardiovascular signs or symptoms occur.

In patients undergoing intra-patient dose escalation or dose reduction during, triplicate 12-lead ECGs must be obtained on Days 1, 8 and 15 of Cycles 1 and 2, pre-dose and 2 h and 4 h after BAL101553 dosing, at each new dose level. From the third cycle onwards, triplicate 12-lead ECGs will only be obtained pre-dose on Day 1.

ECGs performed at Screening, on Day 1 of Cycles 1 and 2, and any abnormal ECGs, will be transmitted to a central ECG laboratory for evaluation, including QTc assessment.

ECGs must always be recorded after at least 5 min rest and while the patient is in a supine or semi-supine position. ECGs must be assessed by the Investigator or his/her designee. The ECG printouts are to be signed and dated by the Investigator or his/her designee. Further instruction and training on handling the device provided and transmitting data will be provided to the study centers prior to study initiation.

The designated physician at the site must review the ECG to assess any abnormalities including prolongation of QTcF. The pre-programmed ECG device must provide automated QTcF intervals.

For an individual patient, significant prolongation of QTcF will be defined as:

- 1. Increase in the QTcF to > 500 ms, or
- 2. Increase in the QTcF of > 60 ms compared to the respective baseline.

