5.5.5.3 Management of QTc prolongation or other significant ECG abnormalities

If significant QTc prolongation is observed, the patient must be monitored by the Investigator and hourly (triplicate) 12-lead ECG need to be obtained until the QTcF has returned to ≤ 470 ms and to ≤ 30 ms increase from baseline. The clinical context and possible factors contributing to QTc prolongations such as electrolyte abnormalities (potassium, calcium or magnesium), concomitant medications, or other clinical factors such as cardiac ischemia will be carefully assessed and any findings documented in the CRF. In addition, a blood sample for determination of BAL101553 concentration must be collected.

Once QTc prolongation has resolved, patients may continue treatment at a lower dose with ECG monitoring frequency as described for Cycle 1 (as in Day 1/Cycle 1 if patients continue treatment at a reduced dose within a treatment cycle). If the ECG obtained in the first cycle after dose reduction are without any QTcF intervals > 500 ms, or increase from baseline > 60 ms, then ECG monitoring in subsequent cycles may follow the normal schedule.

Patients who experience absolute QTcF > 500 ms or QTcF increase from baseline > 60 ms after dose reduction must be discontinued from study.

The clinical management in case of other ECG abnormalities is to be performed at the discretion of the Investigator. Cardiac troponin must be assessed if ECG abnormalities suggestive of cardiac ischemia are observed.

In Phase 1, all significant QTc prolongations or other relevant ECG abnormalities, must be transmitted to the central ECG reading laboratory for evaluation and confirmation.

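### In Phase 1, the central ECG summaries by time point include visits at which only abnormal ECGs are sent for central reading

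*SAP*

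**What the plan says.** SAP 6.3.6 takes RR and QTcF from the CRF, averages the triplicate, and states that values and "changes from baseline will be summarized using standard descriptive statistics by disease subgroup, dose cohort and scheduled time point". The next sentence extends this to the central readings: "The same analysis will be repeated on central ECG data (Heart rate (HR), RR, PR, QRS, QT, QTcB, QTcF". It names no visits and no study phase.

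Which ECGs exist centrally is set elsewhere. Protocol 5.5.5.1 (Phase 1) says: "ECGs performed at Screening, on Day 1 of Cycles 1 and 2, and any abnormal ECGs, will be transmitted to a central ECG laboratory". Footnote 6 to Protocol Table 8 gives the same rule, "ECG from Screening; D1 of Cycles 1, 2; and any abnormal ECG; must be transmitted to a central ECG laboratory for evaluation", and footnote 6 to SAP Table 2 repeats it. Protocol 5.5.5.3 adds: "In Phase 1, all significant QTc prolongations or other relevant ECG abnormalities, must be transmitted to the central ECG reading laboratory".

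The Phase 1 recording schedule in Protocol 5.5.5.1 is wider than the transmission list. Besides Screening and End of Study it has three entries:

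- at the start of the first two cycles: "Day 1 of Cycles 1 and 2: pre-dose; 1 h, 2 h, 4 h, and 8 h after [first] BAL101553 dosing"
- at the visits within those cycles: "Days 8 and 15 of Cycles 1 and 2: pre-dose; 2 h and 4 h after [first] BAL101553 dosing"
- from the third cycle on, one recording before the cycle's first dose

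In Phase 2a (Protocol 5.5.5.2), single ECGs are taken on local devices and no central reading is described.

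**The concern.** A mean by time point is useful if the patients in the row stand for the cohort at that visit. In the central data this holds where every ECG is sent. At the other Phase 1 visits a patient enters the row because the site judged that patient's ECG abnormal. Under Protocol 5.5.5.3 the reason may be QTc prolongation, so entry can depend on the variable being averaged.

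A table built as the SAP is written would place these rows beside the complete ones in the same format. Phase 1 cohorts had 3 to 8 patients (Protocol Appendix 3, Table 22). The number of observations would show that a row is sparse, but not that its patients are there because their ECGs were abnormal. QTcF prolongation is a listed DLT and, if it recurs, a reason to stop treatment, so a reader of the safety tables is likely to look at these rows.

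**Working it through.** The plan gives no figure to reproduce here. The check has two parts: a count from the schedule, and an illustration of how large the shift could be.

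**1. Count of scheduled time points, Phase 1, once-daily dosing, through Cycle 2** (Protocol 5.5.5.1; Protocol 1.5.3 says that twice-daily dosing was not used in Phase 1)

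- All ECGs sent: Screening 1 + Day 1 of two cycles × 5 times = 1 + 10 = 11.
- Sent only if abnormal: Days 8 and 15 × 2 cycles × 3 times = 12.
- Total: 11 + 12 = 23.
- Also sent only if abnormal, outside this count: Day 1 pre-dose of each cycle from Cycle 3, and End of Study.

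**2. Does another rule remove the affected rows?** SAP section 6 keeps unscheduled assessments out of the tables by default. An abnormal ECG recorded at a scheduled Day 8 or Day 15 visit is not unscheduled, so it stays in.

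**3. Possible size of the shift.** All inputs here are assumptions. Baseline and on-treatment QTcF are bivariate normal with the same mean m (410 or 420 ms), the same SD s (15 or 20 ms) and correlation r (0.5 or 0.8). There is no drug effect. An ECG is sent only if QTcF exceeds c = 450 or 470 ms. The documents use both cut-offs, but for other purposes: 450 ms bounds an outlier category in SAP 6.3.6, and 470 ms is the screening limit in exclusion criterion 13. Neither is stated as a transmission rule.

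With a = (c − m)/s and λ = φ(a)/(1 − Φ(a)):

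- proportion sent = 1 − Φ(a)
- mean QTcF among those sent = m + sλ
- mean change from baseline among those sent = (1 − r)sλ (true value 0)

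Worked case: m = 410, s = 20, c = 450 gives a = 2 and λ = 0.0540/0.0228 ≈ 2.37. The mean is 410 + 20 × 2.37 ≈ 457.5 ms. With r = 0.5 the mean change is 0.5 × 20 × 2.37 ≈ 23.7 ms.

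| Cut-off | Proportion sent | Mean QTcF among those sent | Apparent mean change |
|---|---|---|---|
| 450 ms | 0.4% to 6.7% | 454.6 to 458.8 ms | +7.1 to +23.7 ms |
| 470 ms | <0.1% to 0.6% | 473.4 to 476.5 ms | +10.8 to +32.8 ms |

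Under this model the rows are also very thin. Even at 6.7%, a cohort of 8 would supply 8 × 0.067 ≈ 0.5 patients per time point, so a non-empty row would often be one patient. If ECGs are sent for findings unrelated to QTc, more patients contribute and the shift is smaller.

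**The case against.** The strongest reply is that little depends on these rows. CRF means of RR and QTcF are already planned at every scheduled time point, and the central analysis is an additional repeat. The per-patient maximum-value table on CRF and central data, including unscheduled ECGs, is planned too. By-time-point central means feed no DLT, MTD or dose rule. Phase 1 dosing is complete, and Table 22 in Protocol Appendix 3 lists no QTc DLT. All of this stands. It limits the consequence to the reading of a secondary safety table, but it does not make the abnormal-only rows valid.

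Some stronger readings are tempting, and the documents do not support them:

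- **Central data on repeated dosing are lost.** They are not. Day 1 of Cycle 2 follows 28 days of daily dosing, against a half-life of 12 to 24 hours (Protocol 1.5.2.2.3). It is fully transmitted, and its five-point profile is fuller than the three points on Days 8 and 15.
- **The tables will show a QTcF rise of +21 to +41 ms.** That follows if only the largest 5 to 20% of QTcF changes are sent (1.40 × 15 = 21; 2.06 × 20 ≈ 41). The stated rule is any abnormal ECG, which also covers findings unrelated to QTc. A patient with a stable abnormality may be sent repeatedly with a change near zero.
- **Dose-cohort comparisons fail throughout.** Eleven time points through Cycle 2 are complete and remain comparable.
- **The shift table has the same fault.** SAP 6.3.6 specifies it on CRF data.
- **Phase 2a is affected.** No central ECG data are described there.

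**Conclusion.** The concern holds for Phase 1 and for the central summaries by time point only. As written, SAP 6.3.6 calls for central means and changes from baseline at 12 of the 23 scheduled time points through Cycle 2, and at all later visits, where inclusion depends on an abnormal ECG. Those rows could show a spurious QTcF shift. The documents do not fix its size. The +7 to +33 ms range rests on assumed means, SDs and correlations and on assumed selection by absolute QTcF above 450 or 470 ms. Central summaries at Screening and Day 1 of Cycles 1 and 2 are sound, as are all CRF summaries. The SAP should be corrected because the rows are open to misreading and the change is nearly free. No primary or efficacy analysis and no dose decision is affected.

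**What to change.** In SAP 6.3.6:

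1. State that the central summaries by time point cover Phase 1 Screening and Day 1 of Cycles 1 and 2 only.
2. List all other central readings. Use them only in the per-patient maximum-value (outlier) table, with all patients who have on-treatment central ECGs as the denominator.
3. For RR and QTcF at the other visits, rely on the CRF summaries already planned.
4. State that no central ECG analysis applies to Phase 2a.

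The shift table needs no change.

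The cost is a few sentences, with less output and no new data. What is given up is central means at the later Phase 1 visits. SAP 6.3.6 takes only RR and QTcF from the CRF, so PR, QRS, QT and QTcB would have no summary by time point at those visits from either source. Central means there would not have been valid anyway.

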6.3.7 Physical examination

General physical examination assessments will be listed by dose cohort, patient and study day.

6.3.8 Prior and Concomitant medications

Medications and significant non-drug therapies prior to and after the start of the study drug will be listed by patient.

The concomitant medications taken from the start of the study drug (i.e. medications which start before and stop after first study drug administration or medications which start after first study drug administration) will be summarized by Anatomical Therapeutic Chemical (ATC) term and PT.

6.3.9 Chest X-ray/CT

Chest X-ray or CT scan abnormality results will be presented for each patient in a data listing.

6.3.10 ECOG performance status

Eastern Cooperative Oncology Group (ECOG) will be presented for each patient in a data listing.

6.3.11 Transthoracal echocardiography

Transthoracal echocardiography results will be presented for each patient in a data listing.

6.4 Pharmacokinetic analysis

6.4.1 Pharmacokinetic Parameters

PK parameters for BAL101553 and BAL27862 will be calculated from the concentration-time data using a non-compartmental analysis (NCA) method in Phoenix WinNonlin (Version 8 or higher) using Plasma Model 200 - 202 with extravascular dosing or Urine Model. Actual elapsed sampling times relative to time of study drug administration will be used for all parameter estimations.

The following parameters will be derived, as data permit, for Day 1 of Cycles 1 and 2:

C_{max}	Maximum observed concentration
t_{max}	Time to reach maximum observed concentration
AUC_{0-t}	Area under the concentration-time curve from the time of dose administration to the last quantifiable concentration, calculated by linear-log trapezoidal rule
$AUC_{0-\tau}$	Area under the concentration-time curve over a dosing interval, calculated by linear-log trapezoidal rule
$AUC_{0-\infty}$	Area under the concentration-time curve from the time of dose administration extrapolated to infinity, calculated by linear-log trapezoidal rule
$t_{1/2}$	Terminal half-life, calculated as $\ln(2)/\lambda_z$, where λ_z is the terminal phase rate constant
CL/F	Apparent total body clearance (BAL101553 only)
V_z/F	Apparent total volume of distribution (BAL101553 only)
AR	Accumulation ratio, calculated as Cycle 2 Day 1 $AUC_{0-\tau}$ /Cycle 1 Day 1 $AUC_{0-\tau}$
Ae	Total amount of drug excreted in urine over 24 hr
Fe	Fraction of dose excreted in urine over 24 hr

Only data points that describe the terminal elimination log-linear decline will be used in the regression equation for calculation of λ_z . C_{max} and any data point in the distribution phase will not be included in the calculation of λ_z . A minimum of 3 points will be used for determination of the terminal elimination phase rate constant. A time interval of at least 1 half-life will be required to calculate λ_z . An adjusted r^2 value > 0.80 will be considered acceptable for the calculation of the terminal elimination phase rate constant. If adjusted r^2 falls below 0.80, or the above conditions are not met, then the terminal elimination phase rate constant and the associated values of $t_{1/2}$, $AUC_{0-\infty}$, CL/F , and V_z/F will be flagged. If the extrapolated $AUC_{0-\infty}$ is more than 20%, then $AUC_{0-\infty}$, V_z/F and CL/F will be flagged. Flagged values will not be included in the calculation of descriptive statistics.

